Physical activity. In one of our prior studies with CP patients, we assessed physical activity by accelerometry.⁵⁴ In the proposed study, subjects' physical activity will be measured by the Actigraph GT3M accelerometer, worn on the non-dominant wrist. To measure activity and sleep duration, subjects will wear the actigraph monitor continuously for 2 wk. Drs. Roth⁵⁴ and [name] have used these devices before. The actigraphs used are small and unobtrusive, and can provide a reliable and valid estimate of children's moderate-to-vigorous physical activity.⁶⁶⁻⁷⁰ Accelerometer data will be categorized into time spent in sedentary, as well as light, moderate, and vigorous activity using calibration thresholds specifically for children.^{69,71,72} The Physical Activity Checklist Interview,⁷³⁻⁷⁵ will be used to complement actigraphy data with descriptive self-reported assessments of physical activity.

Behavioral and psychosocial measures. Energy intake will be assessed by *Automated Self-Administered 24-Hour Dietary Recall* (ASA24-Kids, <http://appliedresearch.cancer.gov/tools/instruments/asa24/>), which is a validated web-based free method of a 24h dietary recall for children 10 y and older which will be performed at two time points around study visits 0, 18, 36 and 54 wk. At 0, 18 and 36 wk subject's parents will furthermore complete the *Child Eating Behavior Questionnaire* (CEBQ),⁷⁶ or the Adult Eating Behavior Questionnaire (AEBQ) which measures positive and negative eating behaviors (food responsiveness, enjoyment of food, emotional overeating, desire to drink, satiety responsiveness, slowness in eating, emotional undereating and fussiness) and the *Hyperphagia Questionnaire*⁷⁷, a 13- item questionnaire developed for use in patients with Prader-Willi syndrome but that has also been used to study hyperphagic behavior in other populations.⁷⁸⁻⁸⁰ These are all validated questionnaires and we have used them in previous studies.

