Treatment dosage and duration are based on prescribing information and prior successful clinical trial weight loss results.^{31,110} The placebo-control group is an essential arm in this trial as study measures can change over time without drug intervention and it supports the evaluation of efficacy and safety. The drug and placebo kits will be supplied by AstraZeneca, or the current pharmacologic company responsible for ExQW. Exenatide vials or pens 2.0 mg powder for injection will be supplied. All subjects will have weekly phone calls when not coming for a study visit, to check adherence and any potential

adverse effects. Any evidence for adverse effects will be discussed with the PI of each site and safety clinical visits will be considered.

All study medication will be stored/locked in the investigational pharmacy under appropriate temperature conditions. Dispensing and accountability records will be maintained by appropriate staff members.

Analysis

Analysis plan and sample size calculations by Aim.

The research team includes personnel with statistical and data management expertise for overseeing data collection, storage methods, and the following analyses (see letter of support, [name]). Adherence data collected during the placebo run-in phase will be summarized descriptively. All subjects completing the run-in phase will go on to the randomized treatment phase. The primary analyses will use the intention-to-treat (ITT) approach; i.e., subjects will be analyzed according to their randomized assignment regardless of treatment received. In addition, data of all completers will be analyzed separately as a sensitivity analysis. While every attempt will be made to collect complete data and retain all subjects, all sample size and power calculations account for dropout. Statistical methods have been selected to allow for inclusion of partial data. All testing is two-sided and $\alpha=0.05$. Repeated measures analyses will be conducted using SAS (SAS Institute, Inc., Cary, NC, USA) or R (The R Foundation for

Statistical Computing).

Analysis populations: All eligible subjects randomized will be included in the ITT population. The ITT population will be the primary analysis population for all primary, secondary, and tertiary outcomes. The safety population will be the primary population for all safety analyses, and include all subjects who receive at least one dose of study drug or placebo.

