3a: Test GLP1RA treatment on energy homeostasis. Sample: All available EE and energy intake measures from DLW analyses and ASA24 dietary recalls at 0 and 36 wk will be included in the analyses (see Fig. 1). Tertiary outcomes analysis: The tertiary outcomes are change in EE and energy intake from baseline to 36 wk. Separate analyses will be conducted for EE and energy intake. For example for EE, an ANCOVA will be used to model the outcome of change in EE from baseline to 36 wk post-treatment with treatment as the factor of interest and Δ BMI and Δ energy intake included as covariates as both might affect EE independently of drug. A similar ANCOVA will be used to model the outcome of change in energy intake from baseline to 36 wk. Exploratory analyses will examine the change of energy intake after 6 and 18 wk of treatment to estimate effect sizes and inform the design of future studies.

Sample size and power: Assuming a normal distribution of differences, a type I error of 0.05, and a dropout rate of up to 20%, a final evaluable sample size of 19 subjects per group will provide 85% power to detect relative changes (average change divided by the pooled standard deviation (SD) of the change) in EE in relation to energy intake or energy intake in relation to EE of approximately 1 between the two groups. Based on preliminary pooled data from Ambler¹¹⁴ and Eliakim¹¹⁵ et al., the observed

pooled SDs of EE per DLW measures were 162 kcal/d and 155 kcal/d, respectively. Assuming a moderate correlation between baseline and follow-up measures ($r=0.5$), this would correspond to detectable differences of one pooled SD, or 162 kcal/d and 155 kcal/d, respectively. Expected results and benchmarks for success (exploratory efficacy endpoints): We expect that GLP1RA will lead to increased EE adjusted for Δ BMI and Δ energy intake.

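### Energy intake is analysed by a week-0 to week-36 ANCOVA, so randomised subjects with no week-36 recall drop out of that tertiary analysis although a week-18 recall is collected

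*Combined protocol and SAP*

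**What the plan says.** Under Analysis in Section 4, the ITT set is defined: "All eligible subjects randomized will be included in the ITT population". Its reach is then stated: "The ITT population will be the primary analysis population for all primary, secondary, and tertiary outcomes". The same section adds: "Statistical methods have been selected to allow for inclusion of partial data".

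Aim 3a sets the outcomes, "The tertiary outcomes are change in EE and energy intake from baseline to 36 wk", and limits the intake data it will use: "ASA24 dietary recalls at 0 and 36 wk will be included in the analyses". The energy-expenditure (EE) model is an ANCOVA adjusted for change in BMI and change in energy intake. For intake the plan says only "A similar ANCOVA will be used to model the outcome of change in energy intake from baseline to 36 wk", without listing covariates. No imputation or other missing-data method is given. A further sentence reserves intake at weeks 6 and 18 for exploratory work.

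The behavioral measures paragraph describes the 24-hour recall as one "which will be performed at two time points around study visits 0, 18, 36 and 54 wk", and the list in Section 6 agrees (SVs 1, 3, 4 and 5). Neither lists a week-6 recall, so week 18 is the only intermediate value within the randomised phase. Doubly labeled water (DLW) is scheduled at SVs 1 and 4 only.

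By contrast, Aim 1 uses a mixed model so that all follow-up measures enter, and Aim 2 uses similar repeated-measures analyses for its continuous secondary outcomes.

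**The concern.** An ANCOVA on the week-36 change is a complete-case analysis. It does not use the partial data that the Analysis section says its methods were chosen to accept, and the analysed set is smaller than the population named for tertiary outcomes. For EE there is no alternative, because DLW is measured only at baseline and week 36. For intake there is one: the week-18 recall is already collected, and the trial already uses a suitable model in Aims 1 and 2.

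If the intake model mirrors the EE model by adjusting for change in EE, a subject also needs a usable DLW result, which depends on urine samples mailed from home. The analysed set could then be smaller still.

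At stake are some precision and, more importantly, protection against bias if subjects who leave after week 18 differ in intake from those who stay. Intake is one half of the energy-balance hypothesis in Aim 3A, and the plan attaches a power statement to it.

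**Working it through.** **Inputs from the plan.** 24 randomised per arm; dropout up to 20%; 19 evaluable per arm; standardised effect about 1; two-sided alpha 0.05; 85% power (Analysis; Aim 3a). Section 5 expects 48 enrolled and 38 completing.

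**Assumed, because the documents do not say.** How many dropouts have a week-18 recall; the correlations among baseline, week-18 and week-36 intake; and how dropout relates to intake.

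**1. The plan's own figure.** For a two-sample t-test with n = 19 per arm and d = 1, the noncentrality is 1/√(1/19 + 1/19) = √9.5 = 3.08 on 36 df, and power is 0.851 (normal approximation 0.869). Dropout: 24 × 0.8 = 19.2 and 48 × 0.8 = 38.4. The stated 85%, 19 and 38 are all reproduced.

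**2. Who is analysed.** 48 − 38 = 10 randomised subjects, about 5 per arm (10/48 = 21%), would have no week-36 value.

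**3. Precision.** Suppose 19 per arm have both recalls and m more per arm have week 18 only. With ρ the correlation between the week-18 and week-36 changes, the variance of an arm's week-36 mean, in units of σ², is

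(1 − ρ²)/19 + ρ²/(19 + m), against 1/19 = 0.05263 for completers only.

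- m = 2, ρ = 0.3: 0.91/19 + 0.09/21 = 0.05218. Variance is 0.9% lower, effective n 19.2, power 0.854.
- m = 3, ρ = 0.5: 0.75/19 + 0.25/22 = 0.05084. Variance is 3.4% lower, effective n 19.7, power 0.863.
- m = 5, ρ = 0.7: 0.51/19 + 0.49/24 = 0.04726. Variance is 10.2% lower, effective n 21.2, power 0.888.

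**4. Bias.** Simulated true effect 1 SD at weeks 18 and 36; correlation 0.5 with baseline and 0.7 between weeks 18 and 36; dropout logistic in the week-18 change with slope 1 or 2. The completers' ANCOVA here adjusts for baseline only. Estimates are given as absolute size.

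| Assumed dropout | Completers' ANCOVA | Week 18 included |
|---|---|---|
| Low-intake subjects leave drug, high-intake leave placebo; 10% | 0.87–0.92 | about 1.00 |
| Same pattern, 20% | 0.75–0.84 | about 1.00 |
| Same pattern, 20%, half lost before week 18 | 0.75–0.84 | about 0.90–0.93 |
| One common rule in both arms (so more loss on placebo), 10–20% | 0.89–0.97 | about 1.00 |
| Same selection within each arm, equal loss | 1.00 | 1.00 |
| Non-responders leave drug, random loss on placebo, 10–20% | 1.04–1.12 | about 1.00 |

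A simpler mechanism gives a similar picture. Let dropout be 0.6 in the fifth of an arm with the most extreme week-18 change and 0.1 in the rest (0.2 × 0.6 + 0.8 × 0.1 = 0.20), with ρ from 0.3 to 0.7. Completers then give 0.88–0.95 if only placebo is selective, 0.75–0.89 if the arms are selective in opposite directions, and 1.00 if both follow the same rule.

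**The case against.** Several points on the other side stand in whole or in part.

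- **Week 18 is not ignored.** A reader might infer that it is collected and never analysed. Aim 3a does use it, in an exploratory analysis. What is missing is a joint model of weeks 18 and 36.
- **Not everyone who withdraws is lost.** Section 6 asks withdrawing subjects to complete SV4 procedures other than DEXA, and SV4 includes the recall. They are only asked, however, the recall would not be at week 36, and no rule says whether it counts as the week-36 value.
- **ITT is not flatly contradicted.** The Analysis section explains ITT as analysis by assigned arm, which an ANCOVA with missing outcomes can respect. The tension is with the stated population of all eligible randomised subjects and with the partial-data sentence.
- **Early dropout limits the remedy.** Section 7 places gastrointestinal events mainly in the first 6 to 8 weeks. Subjects who leave then have no week-18 recall, so the model reduces their bias at most.
- **The ANCOVA asks a different question.** If it adjusts for change in BMI and EE, it addresses intake in relation to EE, and a week-18 record cannot carry change in EE because no DLW is done then. The simulated model lacks those covariates, so the figures show how selection works and do not measure the error of the planned conditional estimate.
- **The outcome is tertiary**, in an aim described as exploratory.

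**Conclusion.** The point holds as a low-severity improvement to a tertiary analysis. At the plan's own dropout, about 10 of 48 randomised subjects would not contribute to the energy-intake comparison. That number would be lower if exit recalls are obtained and counted, and higher if a DLW result is required. The plan's 85% power figure is correct for 19 evaluable per arm and is not in question.

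The precision gain is small: variance about 1 to 10% lower and power from 0.851 to between 0.854 and 0.888, for ρ of 0.3 to 0.7 and 2 to 5 dropouts per arm with a week-18 recall. The larger benefit is less bias when dropout after week 18 depends on observed intake. Across the logistic settings above, completers' estimates of a true 1 SD effect ran from about 0.75 to 1.12. These are illustrations under assumed mechanisms, not bounds.

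Two stronger readings are tempting. One is that the planned estimate is biased toward no effect. The documents give no dropout mechanism, and the settings above include bias in either direction and none. The other is that adding week 18 removes the bias. It does so only for subjects lost after week 18 whose dropout depends on observed data. Nothing here touches the primary BMI conclusion.

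**What to change.** In Aim 3a, state that the treatment effect on energy intake is estimated with the same type of repeated-measures mixed model as in Aims 1 and 2. Fit it to the week-18 and week-36 recalls with baseline intake and the stratification variables as covariates, take the week-36 treatment contrast as the estimate, and require no DLW value.

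Keep the stated ANCOVA as the analysis conditional on change in BMI and change in EE, and list its covariates explicitly in place of calling it similar to the EE model. State whether a recall obtained at withdrawal is used and to which time point it is assigned.

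The cost is SAP wording only. No new data, visits or subjects are needed.

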4. STUDY DESIGN AND METHODOLOGY

Specific Aims and Hypotheses

Specific Aim 1: To test effects of GLP1RA on hypothalamic obesity prospectively. *We hypothesize that treatment with GLP1RA will significantly reduce adiposity in patients with HO. We furthermore hypothesize that GLP1RA treatment will lead to increased satiety.* To this end, we propose to conduct a double blind, placebo-controlled, randomized trial of once weekly extended release exenatide (ExQW) on metabolic and clinical outcomes. Following baseline testing, 48 patients (10-25y at time of enrollment) with HO will be randomly assigned with equal allocation to ExQW or matching placebo injection for 36 weeks, followed by an 18-week open label extension during which all patients will receive ExQW. Our primary endpoint is percent change in BMI after 36 weeks. Secondary endpoints will include changes in body fat, and satiety by free buffet meal test.

Specific Aim 2: To determine effects of GLP1RA on cardiometabolic risk factors. *We hypothesize that GLP1RA will also lead to (1) favorable changes in blood glucose, lipid profile, and inflammatory marker, and (2) reduced insulin secretion during an oral glucose tolerance test.* In the same cohort, we will examine changes in blood glucose, lipid profile, inflammatory markers, and insulin resistance by testing insulin secretion during an oral glucose tolerance test after adjustment for glucose response and adiposity.

Specific Aim 3: To explore additional outcome measures, and predictors of treatment responses. HO represents a disorder of energy homeostasis.

Aim 3 A: *To test the hypothesis that GLP1RA will normalize homeostasis by increasing EE in relation to energy intake.* This and prior hypotheses allow us to test potential predictors of treatment outcomes.

Aim 3 B: *To test the hypotheses that (1) a lower hypothalamic lesion score and (2) lower fasting serum leptin as well as (3) higher pretreatment hyperphagia will be associated with better BMI outcomes.*

The study will include brain lesion scoring, behavioral and hormonal measures, free-living total daily energy expenditure by doubly labeled water (DLW), energy intake by 24h dietary recall, and activity by actigraphy.

Overview/Scope

Study Design

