Table 1. Summary of Study Measures and Outcomes and Their Use in the Proposed Research

Measure	Domain	Instrument	Aim	Role/Application
$\Delta\text{BMI}\%$	Adiposity	Anthropometry	1	Primary outcome
Total body fat mass	Body composition	DEXA	1	Secondary outcome
Fat and total calorie intake	Post test meal satiety assessment	Free buffet meal analysis	1	Secondary outcome
Glucose tolerance	Glucose tolerance, MetS	Glucose at 0', 120' (OGTT)	2	Secondary outcome
HDL, triglycerides	MetS	Fasting lipids	2	Secondary outcome
hsCRP	Inflammation	hsCRP at fasting time point	2	Secondary outcome
Free living EE	Energy homeostasis	Doubly labeled water	3	Tertiary outcome
Energy intake	Energy intake	24h dietary recall (ASA24)	3	Tertiary outcome
Leptin, adiponectin, sOB-R, α -MSH, HOMA-IR, WBISI	Energy homeostasis, leptin sensitivity, and insulin resistance	Baseline and stimulated hormones	3	Tertiary outcomes and predictors

Aim 1: To test effects of GLP1RA on hypothalamic obesity prospectively.

Sample: Available anthropometry measures will be included in the analyses (see also Fig. 1 below).

Primary outcome analysis: For efficacy analysis the primary outcome is % change in BMI from week 0 (baseline) to 36 wk. A piecewise (separating the randomized and run out phases) linear mixed-effects model¹¹¹ will be fit with % change in BMI from baseline to 36 wk as the outcome; treatment, time, and the interaction between treatment and time as factors of interest; and randomization stratification variables (site, age, and gender) included as covariates. This model is a generalization of analysis of covariance (ANCOVA) that allows all follow-up repeated measures to be included.

Table 2. Additional Descriptive Parameters, Predictors and Covariates used in Study

Measure	Domain	Instrument	Aim
ΔBMI , ΔBMI z-score	Adiposity	Anthropometry	1
Subjective appetite	Hunger and fullness rating	Visual analog scale	1
Syst. & diast. BP	CVD risk factor, MetS	Ambulatory BP	2
Exercise	Physical activity measure	Actigraphy ^{112,113}	3
Energy intake	Energy intake	24h dietary recall	3
Eating behavior	Assessment of overeating and food reward	Overeating (CEBQ), ⁷⁶ & hyperphagia. ⁷⁷	3
Brain lesion score, hypothalamic region and residual lesion volumes	Structural lesion in the pituitary-hypothalamic area	Brain MRI images	3

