3b: Determine predictors of GLP1RA treatment success. Sample: Pretreatment metabolic parameters and EE measures from DLW analyses (see Fig. 1), and all available outcomes measures will be included in the analyses (collected at 0 and 36 wk). Outcome measures and exploratory analyses: Potential predictors will be considered one at a time. Potential predictors include a hypothalamic lesion score; hyperphagia; EE; and the metabolic predictors leptin, adiponectin, sOB-R, α -MSH, HOMA-IR, WBISI including a leptin/Ob-R ratio.²⁰⁴ In addition to examining the relationship between the post-surgery lesion score (=standard approach for all subjects) and the response to GLP1RA treatment, we will perform a measurement study using high resolution images that would allow parcellation of the hypothalamus and surrounding areas. We expect that we will obtain images in the required high resolution quality in a subgroup of patients (50%; $n=24$). We will use these images for exploratory volumetric as well as topographic studies and will test if lesion volume or deficiencies in certain brain areas are associated with obesity outcomes or response to treatment using analyses similar to those described for lesion score. These exploratory measurement studies may be important for generating future hypotheses. A linear mixed-effects model will be fit with % change in BMI from baseline to follow-up as the outcome; treatment, time, the interaction between treatment and time, the potential predictor, and interactions between the potential predictor and treatment, time and treatment x time as factors of interest. Covariates and within-subject correlation matrix are as described for Specific Aim 1. Exploratory analyses will examine eating behavior and fat and total calorie intake as additional covariates. A contrast based on the interaction between the potential predictor and treatment x time will be used to estimate the direction and magnitude of the potential predictor on treatment response at 36 wk. Predictors will be standardized to be unitless, dividing by the SD to rank magnitudes and compare across predictors.

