Sample size and power: For this exploratory aim no formal power calculations are conducted. Analyses will focus on the direction and magnitude of effects for use in planning future studies. Expected results and interpretation: We expect the degree of % change in BMI reduction (1) is positively associated with the degree of hyperphagia assessed by CEBQ, and (2) higher energy expenditure at baseline; (3) is negatively associated with insulin and leptin resistance as measured by WBISI, HOMA-IR, and leptin at baseline, and (4) is negatively associated with the post-operative hypothalamic lesion score (e.g., a higher score indicating greater hypothalamic damage).

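### Aim 3b fits baseline leptin and total energy expenditure without any body-size term, so their slopes would absorb part of any effect of size on treatment response

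*Combined protocol and SAP*

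**What the plan says.** Section 4, Analysis, Aim 3b sets out one model per predictor: "Potential predictors will be considered one at a time". The list includes a lesion score, then "hyperphagia; EE; and the metabolic predictors leptin, adiponectin, sOB-R" and others, among them a leptin/Ob-R ratio. Baseline BMI, weight, height and fat mass are not on it.

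Each model has percent change in BMI as outcome and contains the predictor with its interactions with treatment, time and treatment by time. The estimate of interest is stated: "A contrast based on the interaction between the potential predictor and treatment x time will be used". For adjustment, "Covariates and within-subject correlation matrix are as described for Specific Aim 1", and Aim 1 has the "randomization stratification variables (site, age, and gender) included as covariates". One extension is offered: "Exploratory analyses will examine eating behavior and fat and total calorie intake as additional covariates". That refers to food eaten, not body fat. Slopes are then divided by the predictor's SD so that predictors can be ranked against each other.

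Under Energy expenditure measures, total EE is in kcal/day, not indexed to body size. Specific Aim 3 B words the leptin question as a hypothesis: "lower fasting serum leptin as well as (3) higher pretreatment hyperphagia will be associated with better BMI outcomes". The expected results for Aim 3b treat baseline leptin as a measure of leptin resistance and expect a greater BMI reduction with "higher energy expenditure at baseline".

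**The concern.** Patients are aged 10 to 25, so body size will vary widely. If leptin rises with fat mass and total EE with body mass, the raw values are partly measures of size. Any tendency of larger or smaller patients to respond differently would then appear as a leptin effect or an EE effect, and the ranking could list two proxies for size as separate predictors.

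The plan accepts the principle elsewhere. Aim 2 adjusts insulin secretion for adiposity, the section on OGTT derived measures adjusts changes in glucose metabolism for change in BMI, and Aim 3a includes change in BMI in the model for change in EE. Aim 3b has no baseline counterpart, although the visit schedule in section 6 places a whole-body DEXA at study visit 1.

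At stake is interpretation. Aim 3b is meant to inform later studies, and a predictor credited with an effect that belongs to body size would misdirect them.

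**Working it through.** **The plan's own figure.** Aim 3b states no power, so the sample size comes from Aim 1: 24 per group, up to 20% dropout, 19 evaluable, 85% power for an effect of 1 SD.
- 19 / (1 − 0.20) = 23.75, rounded up to 24 per group.
- Noncentrality 1/√(2/19) = 3.08 on 36 degrees of freedom gives 85.1% power for a two-sided t-test at 0.05 (86.9% by normal approximation).

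Both figures reproduce. I use 2 × 19 = 38 patients below.

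**Assumptions not in the documents.** Let S be body size or fat mass and P the predictor, both in SD units, with correlation ρ. Size changes the treatment effect by γ outcome (residual) SDs per SD of S. P has no effect of its own. The model is simplified to one week-36 outcome without site, age and gender. In the plan those enter as covariates without treatment interactions of their own, so they would not remove moderation by size.

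**What the planned slope estimates.** With S left out, the P-by-treatment slope is γ × cov(S,P)/var(P) = ργ. Simulated mean slopes agree:
- γ = 0.5: ργ = 0.25, 0.35 and 0.425 at ρ = 0.5, 0.7 and 0.85; simulated 0.24, 0.36 and 0.42.
- γ = 1.0: ργ = 0.50, 0.70 and 0.85; simulated 0.50, 0.71 and 0.86.

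**How often the leptin-by-treatment term is significant** (38 patients, two-sided 0.05, 4,000 simulated trials per cell):

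| γ | ρ = 0.5 | ρ = 0.7 | ρ = 0.8 |
|---|---|---|---|
| 0.2 | 5% | 7% | 8% |
| 0.3 | 7% | 10% | 10% |
| 0.6 | 13% | 21% | 26% |
| 1.0 | 26% | 46% | 57% |

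Repeat simulations agree within a few points. They reach at most about 11% for γ of 0.2–0.3, and give 11–24%, 22–43% and 27–54% at the three correlations for γ of 0.6–1.0.

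**After adjustment.**
- With S and S-by-treatment in the model, the spurious slope is about 0 and the rejection rate returns to 4–6%.
- S as a main effect alone does not help: at γ = 0.5 and ρ = 0.7 the slope stays at 0.36, with 16% significant.

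**Cost in precision.** The standard error is multiplied by 1/√(1 − ρ²), which is 1.15, 1.40 and 1.67 at ρ = 0.5, 0.7 and 0.8. If leptin truly modifies response by 0.6 SD per SD and fat mass does not, power falls from about 40% to 30%, 22% and 16%.

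**Direction.** The plan expects lower leptin and higher EE to go with better response. If both rise with size, then:
- larger patients responding better would favour the EE expectation and count against the leptin one;
- smaller patients responding better would do the reverse.

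**The case against.** The strongest reply is that Aim 3b asks which baseline measures predict response, and leptin that predicts through fat mass still predicts. On that reading the rates in the table are power to detect a real association, not an error rate. The aim is also labelled exploratory, has no formal power calculation, and focuses on direction and magnitude. This stands, and it is why the planned models should be kept. It does not cover the reading of leptin as leptin resistance, or the ranking, and magnitude is exactly what an omitted size effect distorts.

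A second reply is that adjustment may remove too much. The Introduction presents leptin resistance, low EE and increased fat storage together as consequences of hypothalamic damage, so fat mass may lie on the causal pathway. This also stands, and it argues for showing both estimates.

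Some stronger readings are tempting but not supported:
- A reader might infer that the trial would wrongly support both the leptin and the EE hypotheses. One size effect would tend to support one and contradict the other.
- A reader might infer that the plan gives EE a mechanistic meaning as a metabolic predictor. It lists EE apart from the metabolic predictors and says only that higher values should go with better response.
- A reader might take 57% as the expected error rate. At γ = 1.0 the moderation per SD of fat mass equals the whole 1 SD treatment effect in the sample-size calculation. Nothing in the documents shows that moderation of this size, or any, exists.

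Part of the Aim 1 model description, including the correlation matrix, is not in the text available to me. The covariate list reads as complete.

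**Conclusion.** The concern holds in a limited form. The Aim 3b models cannot separate leptin or total EE from body size, and their slopes carry a fraction ρ of any moderation by size. That fraction follows algebraically. Whether it matters depends on two quantities the documents do not give: the correlation with size and the strength of moderation. Over assumed correlations of 0.5–0.8, the chance of a significant leptin term with no leptin effect of its own is about 5–11% for weak moderation (0.2–0.3 SD per SD) and about 13–57% for strong moderation (0.6–1.0). Adjustment brings it back to about 5%. The rejection rates were worked out for leptin; for EE the same formula applies at whatever its correlation with size proves to be.

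This is a worthwhile, inexpensive improvement to an exploratory analysis. It does not touch the primary result, and it does not make the planned associations invalid as prediction.

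**What to change.** Keep the one-at-a-time models and describe their results as predictive associations. Prespecify beside them:

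- leptin and leptin/Ob-R models that add baseline DEXA fat mass, with its interactions with treatment, time and treatment by time;
- an EE model that adds baseline DEXA fat-free mass with the same interactions;
- baseline fat mass or BMI as a benchmark in the predictor ranking.

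Call a leptin or EE effect independent of body size, or leptin a marker of leptin resistance, only where the adjusted estimate is shown alongside. Report the observed correlation of each predictor with the size measure, so that readers can judge what the data can separate.

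No new visits, patients or measurements are needed. The cost is a few model terms and less precise adjusted estimates, with standard errors about 15–67% larger at correlations of 0.5–0.8. Adjustment may also take away part of a genuine effect if fat mass is on the pathway, so neither estimate should be reported alone.
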